10.7 Statistical tests

A one-way analysis of variance (ANOVA) model will be used to test whether changes in pain scores differ by study group. The outcome variable for the model will be the change in pain scores, and the independent variables will be indicators of each study group. The overall F-test for study group will be used to determine whether study groups differ with respect to mean changes in visual pain scores. If the F-test is significant, then follow up tests comparing each set of groups will be conducted using the Bonferroni-adjusted Type I error rate of 1.7%.

10.8 Suspension of research

There will be no stopping rules in this study as all medications are FDA approved and safe for patient use.

If a patient, at any point in the course of their treatment demonstrates a significant adverse event related to the study medication, then the adverse event will be addressed.

11.0 Risks

Loss of confidentiality will be minimized as the research team will only have access to the research data and all information will be kept in a shared research file in HersheyMed.net on a password-protected computer, in the Orthopaedic research office locked filing cabinets.

Subjects will be assigned to a treatment program by chance. The treatment received may prove to be less effective or to have more side effects than the other research treatment(s) or other available treatments.

Ethyl Chloride - freezing may alter skin pigment

Kenalog - joint tissue damage, swelling in your veins, allergic reaction, infection, increase in blood sugar.

Lidocaine - itching, rash, swelling of the skin, pain at the injection site, numbness, dizziness, and allergic reactions. Rarely, when injected into the blood stream lidocaine can cause confusion, coma, seizures, respiratory arrest, heart beat irregularities, and toxicities; however, in this study lidocaine will not be injected into your bloodstream.

Nerve damage for a period of time after the injection.

12.0 Potential Benefits to Subjects and Others

12.1 Potential Benefits to Subjects

The treatment received may prove to be less or more effective or to have more side effects than the other research treatment or other available treatments.

12.2 Potential Benefits to Others

The potential benefit may be a way to reduce healthcare cost by decreasing the over-utilization of unnecessary materials/procedures. The results of this study will guide future treatment decisions.

13.0 Sharing Results with Subjects

The results will not be shared.

14.0 Subject Stipend (Compensation) and/or Travel Reimbursements

Not applicable

15.0 Economic Burden to Subjects

15.1 Costs

All procedures are standard of care and will be billed to insurance. The subjects will be liable for any copays, deductibles, or other fees associated with their insurance policy.

15.2 Compensation for research-related injury

It is the policy of the institution to provide neither financial compensation nor free medical treatment for research-related injury. In the event of injury resulting from this research, medical treatment is available but will be provided at the usual charge. Costs for the treatment of research-related injuries will be charged to subjects or their insurance carriers.

16.0 Resources Available

16.1 Facilities and locations

Research will be conducted at the Penn State Hershey Bone and Joint Institute.

16.2 Feasibility of recruiting the required number of subjects

The Penn State Hershey Bone and Joint Institute cares for many patients with shoulder problems that need to get steroid injections to relieve pain. The PI does 1-2 injections per clinic and has 2 clinics a week. After 52 weeks the sample size would be around 150, which is above the 138 subject sample size calculated by the edited stats analysis.

16.3 PI Time devoted to conducting the research

[name] has research time determined in his agreement with the Orthopaedic Department.

16.4 Availability of medical or psychological resources

If any medical or psychological care is needed for a subject, they will be directed for standard of care treatment at Hershey Medical Center.

16.5 Process for informing Study Team

All team members have been given copies of all IRB approved documents – protocol, data collection tools, approval memos, etc. The team meets regularly to review data and any updates.

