7.2 Study Procedures

The study consists of one visit in clinic during their standard of care visit. Patients will be given information about the study and asked to participate. If eligible, based on inclusion and exclusion criteria, informed consent will be obtained at the time of the screening visit and the patient will be enrolled in the study.

After obtaining informed consent, the patient will be asked to rate their current pain on a visual 1-10 point scale before injection. They will then be randomized to one of three treatment groups. The study investigator will randomly draw a sealed envelope containing one of the three treatment groups. The sealed envelopes will be stored in a secure area within the clinic practice site. The subject will be randomized to one of three groups:

- Group A=Injection of 1 ml of 40 mg Kenalog combined with 4 ml of 1% lidocaine
- Group B=Injection of 1 ml of 40 mg Kenalog combined with 4 ml of 1% lidocaine after 2 ml in subcutaneous injection
- Group C=Injection of 1 ml of 40 mg Kenalog combined with 4 ml of 1% lidocaine after applying ethyl chloride spray for 3 seconds

The needle size will be standardized:

- 25 gauge needle for the subcutaneous lidocaine injection
- 21 gauge needle for the combined injection

Immediately after and ten minutes after the injection is completed, they will also be asked to rate pain on the same 1-10 visual scale.

No long-term follow-up will be conducted.

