7.4.5 Blinding of the Test Article

Not applicable.

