7.4.6.3 Preparation and Dispensing

The study drug will be prepared by an investigator following standard of care protocols. Subject randomization will be performed prior to dispensing of any study drugs. Once the needle is in the proper location, the solution of steroid will be injected slowly. A 2 mL solution of 1% lidocaine without epinephrine will be injected subcutaneously prior to the steroid injection if the subject is randomized into group B. If subject is in group C, ethyl chloride spray will be applied for 3 seconds prior the steroid injection.

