19.7 Stopping Rules

The study will be stopped if one method is found to be clearly superior or if there are adverse reactions.

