20.0 Study Monitoring, Auditing and Inspecting

20.1 Study Monitoring Plan

20.1.1 Quality Assurance and Quality Control

Study data will be recorded and kept in a shared folder on hersheymed.net in a restricted file accessible by investigators on the study. The Principal Investigator will oversee all aspects of the study including monitoring.

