20.5 Access to data and/or specimens

Data will only be accessible by investigators listed on the study.

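### The unmasked team reviews accumulating data regularly, and no text limits that review to pooled or safety data, while an undated superiority stop conflicts with the no-stopping-rules statement

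*Combined protocol and SAP*

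**What the plan says.** **Review.** Section 16.5, on informing the study team, states: "The team meets regularly to review data and any updates". It does not say how often, which data, or whether they are pooled or split by group.

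**Access.** Section 20.1.1: "Study data will be recorded and kept in a shared folder on hersheymed.net in a restricted file accessible by investigators on the study". Section 20.5: "Data will only be accessible by investigators listed on the study". Section 10.5, which asks who reviews the data, is answered as not applicable.

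**Roles.** Masking (7.4.5) is marked not applicable. Section 7.2: "The study investigator will randomly draw a sealed envelope containing one of the three treatment groups". Section 7.4.6.3: "The study drug will be prepared by an investigator following standard of care protocols". Section 16.2: "The PI does 1-2 injections per clinic and has 2 clinics a week". Section 20.1.1 also puts the PI in charge of monitoring. Consent is obtained by a member of the research team (5.1.1.2, 5.2.1). Who takes the pain rating is not stated.

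**Looks and stopping.** Section 10.6 plans one interim analysis at 50% of patients. Section 10.2 says the data reviewed include adverse effects, and 10.7 lists the pain ANOVA by group as the test in the monitoring section. Section 19.7: "The study will be stopped if one method is found to be clearly superior", with adverse reactions as a second ground. Section 10.8 says the study has no stopping rules.

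**Error rate.** Section 8.2 sets 1.7% for each of three pairwise comparisons and presents this as holding the study at 5% overall.

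**The concern.** Pain is the only outcome. The patient reports it in the clinic, immediately and ten minutes after an unmasked injection. If the people treating the next patient know which method is ahead, that knowledge can reach the next score through how the method is described, how the injection is given or how the rating is prompted. It can also reach the envelope draw, which an investigator performs. None of this requires early stopping.

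The second issue is error control. The Bonferroni correction in 8.2 pays for three comparisons at one analysis. It does not pay for further looks at the group comparison if such a look can end the study. Section 19.7 opens that possibility without naming a time, a threshold or a decision-maker.

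This is distinct from how the 50% analysis in 10.6 is specified. Repairing that analysis would leave 16.5, 20.1.1 and 20.5 as they are.

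**Working it through.** **1. Do the plan's own inputs reproduce?** From 8.2: difference 2, SD 3, 50 per group, three tests. Alpha per test = 0.05/3 = 0.0167, taken as two-sided because sidedness is not stated. Standard error = 3 × √(2/50) = 0.60. With 98 degrees of freedom the critical t is 2.436. Noncentrality = 2/0.60 = 3.33, and noncentral-t power is 81.3%. This agrees with the stated 80%.

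**2. What is written and what is inferred?**

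| Element | Status |
|---|---|
| Team meets regularly to review data | Stated, 16.5 |
| Listed investigators have access | Stated, 20.1.1 and 20.5 |
| An investigator draws envelopes; the PI injects | Stated, 7.2 and 16.2 |
| No masking | Stated, 7.4.5 |
| Meetings see pain by group | Not stated and not excluded |
| A meeting can stop the study | Not stated; 19.7 sets no timing and 10.8 says no stopping rules |
| Review limited to pooled or safety data | Not stated; the wording in 10.2 is not exclusive |

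**3. What would unplanned looks cost if they could stop the study?** The number of looks is not in the documents, so this is a range. Assumptions: no true difference, normal outcomes, 50 per arm at the end and equally spaced looks. At each look the rule in 8.3 is applied: F-test at 5%, then any pair at 0.05/3 with pooled variance. The study may stop on significance. Results from 40,000 simulated trials, with simulation error about 0.1 to 0.2 points:

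| Looks, including the final | Chance of at least one false claim |
|---|---|
| 1 | 4.3% |
| 2 (the 50% look plus final) | 7.3% |
| 4 | 11.4% |
| 6 | 14.0% |
| 12 (about monthly over the 52 weeks in 16.2) | 19.2% |

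With ordinary two-sample t-tests for the pairs (alpha 1.7%), the figures for 4 and 12 looks are 10.4% and 17.8%. The two-look row belongs to the 10.6 analysis and is shown only for reference.

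**4. What would feedback bias cost?** Suppose knowing the trend shifts scores in one arm by *s* points during the second half of recruitment. The final difference moves by *s*/2. The rejection probability for that pair, with no true difference, is P(|T| > 2.436), where T is noncentral t with 98 degrees of freedom and noncentrality (*s*/2)/0.60.

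| *s* | Final bias | Noncentrality | False-positive rate, one pair |
|---|---|---|---|
| 0 | 0 | 0 | 1.7% |
| 0.5 | 0.25 | 0.417 | 2.6% |
| 1 | 0.5 | 0.833 | 5.9% |

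The size of *s* is assumed. The documents give no basis for it. These rates are for the pairwise test alone; requiring the F-test first lowers the last one to about 5.5%.

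**The case against.** Section 16.5 is a general statement about keeping the team informed. It does not mention pain, groups or comparison. The only section naming reviewed data (10.2) names adverse effects, and the only scheduled analysis before the end is at 50%. A reader might infer that investigators see the pain comparison at every meeting and may stop the study at any of them. The documents do not support that: neither practice is written anywhere, and 10.8 denies that stopping rules exist. This part of the objection stands.

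Other parts stand too.

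- A reader might infer that the investigators also obtain consent and take the ratings. The documents assign consent to a member of the research team and leave the rater unnamed.
- Section 9.0 refers data management to a separate Research Data Plan Review Form, which may contain access limits not visible here.
- Section 20.1.2 gives a coordinator and a monitor a role with adverse event forms, so the investigators-only wording in 20.5 is not the full picture.
- The figures for repeated looks assume formal tests at each meeting, which no section provides for.

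What does not stand is the suggestion that silence is enough. The data described in 10.2 are not confined to safety, 10.7 places the pain ANOVA in the monitoring section, and 19.7 leaves its superiority stop undated. In an open trial with one subjective endpoint, the protocol text should state the limit.

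**Conclusion.** The gap is real, and it is one of missing restriction. As written, the plan lets the people who allocate and inject have access to group-linked pain data while recruitment continues, and it has the team review data regularly. Nothing in the protocol text keeps the comparison from them. Separately, 19.7 and 10.8 contradict each other, and 19.7 has no timing and no link to 10.6.

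The size cannot be fixed from the documents. About 11% to 19% for 4 to 12 looks depends on assumed looks, formal testing and stopping at each. The range of 2.6% to 5.9% for one pair depends on an assumed final bias of 0.25 to 0.5 points. They show that the 5% in 8.2 would not survive such practices; they do not estimate what this study will do. The change is worth making because it is cheap and closes a route to bias on the only endpoint.

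**What to change.** - **16.5:** state that team meetings review only enrolment, completeness of forms and adverse events.
- **20.1.1 and 20.5:** state that files linking pain scores to group, and any by-group pain summary, are held by an existing team member who does not allocate, inject or take scores. They are not shown to those who do until the last subject's ten-minute rating. The documents name a research coordinator but no study statistician, and do not say who takes scores, so the holder must be chosen with that in mind. Align the Research Data Plan Review Form with this text.
- **8.3 or 10.7:** state that pain is compared by group only at analyses named in the plan.
- **10.6, 10.8 and 19.7:** reconcile them. If the result includes a superiority stop, give its timing, its decision-maker and how it fits within the 5% in 8.2.

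The cost is a few sentences and a folder-permission change, with no added patients. No added staff are needed provided a suitable team member is available. Investigators lose sight of the running result. In an open clinic the injector may still see individual scores, so the change hides the aggregate comparison only.

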17.0 Other Approvals

17.1 Other Approvals from External Entities

Not applicable.

17.2 Internal PSU Committee Approvals

Check all that apply:

Anatomic Pathology – Hershey only – Research involves the collection of tissues or use of pathologic specimens. Upload a copy of the Use of Human Tissue For Research Form on the “Supporting Documents” page in CATS IRB. This form is available on the IRB website at: <http://www.pennstatehershey.org/web/irb/home/resources/forms>

Animal Care and Use – All campuses – Human research involves animals and humans or the use of human tissues in animals

Biosafety – All campuses – Research involves biohazardous materials (human biological specimens in a PSU research lab, biological toxins, carcinogens, infectious agents, recombinant viruses or DNA or gene therapy).

Conflict of Interest Review – All campuses – Research has one or more of study team members indicated as having a financial interest.

Radiation Safety – Hershey only – Research involves research-related radiation procedures. All research involving radiation procedures (standard of care and/or research-related) must upload the Radiation Review Form on the “Supporting Documents” page in CATS IRB. This form is available on the IRB website at: <http://www.pennstatehershey.org/web/irb/home/resources/forms>

IND/IDE Audit – All campuses – Research in which the PSU researcher holds the IND or IDE or intends to hold the IND or IDE.

Scientific Review – Hershey only – All investigator-written research studies requiring review by the convened IRB must provide documentation of scientific review with the IRB submission. The scientific review requirement may be fulfilled by one of the following: (1) external peer-review process; (2) department/institute scientific review committee; or (3) scientific review by the Clinical Research Center Advisory committee. NOTE: Review by the Penn State Hershey Cancer Institute Scientific Review Committee is required if the study involves cancer prevention studies or cancer patients, records and/or tissues. For more information about this requirement see the IRB website at:
<http://www.pennstatehershey.org/web/irb/home/resources/investigator>

18.0 Multi-Site Research

18.1 Communication Plans

not applicable

18.2 Data Submission and Security Plan

not applicable

18.3 Subject Enrollment

not applicable

18.4 Reporting of Adverse Events and New Information

not applicable

18.5 Audit and Monitoring Plans

not applicable

19.0 Adverse Event Reporting

19.1 Adverse Event Definitions

Adverse event	Any untoward medical occurrence associated with the use of the drug in humans, whether or not considered drug related
Adverse reaction	Any adverse event caused by a drug
Suspected adverse reaction	Any adverse event for which there is a reasonable possibility that the drug caused the adverse event. Suspected adverse reaction implies a lesser degree of certainty about causality than "adverse reaction". 
• Reasonable possibility. For the purpose of IND safety reporting, "reasonable possibility" means there is evidence to suggest a causal relationship between the drug and the adverse event.
Serious adverse event or Serious suspected adverse reaction	Serious adverse event or Serious suspected adverse reaction: An adverse event or suspected adverse reaction that in the view of either the investigator or sponsor, it results in any of the following outcomes: Death, a life-threatening adverse event, inpatient hospitalization or prolongation of existing hospitalization, a persistent or significant incapacity or substantial disruption of the ability to conduct normal life functions, or a congenital anomaly/birth defect. Important medical events that may not result in death, be life-threatening, or require hospitalization may be considered serious when, based upon appropriate

	medical judgment, they may jeopardize the patient or subject and may require medical or surgical intervention to prevent one of the outcomes listed in this definition.
Life-threatening adverse event or life-threatening suspected adverse reaction	An adverse event or suspected adverse reaction is considered “life-threatening” if, in the view of either the Investigator (i.e., the study site principal investigator) or Sponsor, its occurrence places the patient or research subject at immediate risk of death. It does not include an adverse event or suspected adverse reaction that had it occurred in a more severe form, might have caused death.
Unexpected adverse event or Unexpected suspected adverse reaction.	An adverse event or suspected adverse reaction is considered “unexpected” if it is not listed in the investigator brochure, general investigational plan, clinical protocol, or elsewhere in the current IND application; or is not listed at the specificity or severity that has been previously observed and/or specified.

For device studies, incorporate the following definitions into the below responses, as written:	
Unanticipated adverse device effect	Any serious adverse effect on health or safety or any life-threatening problem or death caused by, or associated with, a device, if that effect, problem, or death was not previously identified in nature, severity, or degree of incidence in the investigational plan or IDE application (including a supplementary plan or application), or any other unanticipated serious problem associated with a device that relates to the rights, safety, or welfare of subjects.

19.2 Recording of Adverse Events

All adverse events (serious or non-serious) and abnormal test findings observed or reported to study team believed to be associated with the study drug(s) or device(s) will be followed until the event (or its sequelae) or the abnormal test finding resolves or stabilizes at a level acceptable to the investigator.

An abnormal test finding will be classified as an adverse event if one or more of the following criteria are met:

- The test finding is accompanied by clinical symptoms
- The test finding necessitates additional diagnostic evaluation(s) or medical/surgical intervention; including significant additional concomitant drug treatment or other therapy

NOTE: Simply repeating a test finding, in the absence of any of the other listed criteria, does not constitute an adverse event.

- The test finding leads to a change in study drug dosing or discontinuation of subject participation in the clinical research study

The test finding is considered an adverse event by the investigator.

19.3 Causality and Severity Assessments

The investigator will promptly review documented adverse events and abnormal test findings to determine 1) if the abnormal test finding should be classified as an adverse event; 2) if there is a reasonable possibility that the adverse event was caused by the study drug(s) or device(s); and 3) if the adverse event meets the criteria for a serious adverse event.

If the investigator's final determination of causality is “unknown and of questionable relationship to the study drug(s) or device(s)”, the adverse event will be classified as associated with the use of the study drug(s) or device(s) for reporting purposes. If the investigator's final determination of causality is “unknown but not related to the study drug(s) or device(s)”, this determination and the rationale for the determination will be documented in the respective subject's case history.

19.4 Reporting of Adverse Reactions and Unanticipated Problems to the FDA

19.4.1 Written IND/IDE Safety Reports

Not applicable.

19.4.2 Telephoned IND Safety Reports – Fatal or Life-threatening Suspected Adverse Reactions

Not applicable.

19.5 Reporting Adverse Reactions and Unanticipated Problems to the Responsible IRB

In accordance with applicable policies of The Pennsylvania State University Institutional Review Board (IRB), the investigator will report, to the IRB, any observed or reported harm (adverse event) experienced by a subject or other individual, which in the opinion of the investigator is determined to be (1) unexpected; and (2) probably related to the research procedures. Harms (adverse events) will be submitted to the IRB in accordance with the IRB policies and procedures.

